5.2 SAFETY PARAMETERS AND DEFINITIONS

Safety assessments will consist of monitoring and recording AEs, including SAEs and AEs of special interest, performing protocol-specified safety laboratory assessments, measuring protocol-specified vital signs, and conducting other protocol-specified tests that are deemed critical to the safety evaluation of the study.

Certain types of events require immediate reporting to the Sponsor, as outlined in Section [5.4](#).

5.2.1 Adverse Events

According to the ICH guideline for GCP, an AE is any untoward medical occurrence in a clinical investigation subject administered a pharmaceutical product, regardless of causal attribution. An AE can therefore be any of the following:

- Any unfavorable and unintended sign (including an abnormal laboratory finding), symptom, or disease temporally associated with the use of a medicinal product, whether or not considered related to the medicinal product
- Any new disease or exacerbation of an existing disease (a worsening in the character, frequency, or severity of a known condition) (see Section [5.3.5.9](#) for more information)
- Recurrence of an intermittent medical condition (e.g., headache) not present at baseline
- Any deterioration in a laboratory value or other clinical test (e.g., ECG, X-ray) that is associated with symptoms or leads to a change in study treatment or concomitant treatment or discontinuation from study drug
- Adverse events that are related to a protocol-mandated intervention, including those that occur prior to assignment of study treatment (e.g., screening invasive procedures such as biopsies)

5.2.2 Serious Adverse Events (Immediately Reportable to the Sponsor)

An SAE is any AE that meets any of the following criteria:

- Is fatal (i.e., the AE actually causes or leads to death)
- Is life threatening (i.e., the AE, in the view of the Investigator, places the subject at immediate risk of death)

This does not include any AE that, had it occurred in a more severe form or was allowed to continue, might have caused death.

- Requires or prolongs inpatient hospitalization (see Section [5.3.5.10](#))

- Results in persistent or significant disability/incapacity (i.e., the AE results in substantial disruption of the subject's ability to conduct normal life functions)
- Is a congenital anomaly/birth defect in a neonate/infant born to a mother exposed to study drug
- Is a significant medical event in the Investigator's judgment (e.g., may jeopardize the subject or may require medical/surgical intervention to prevent one of the outcomes listed above)

The terms "severe" and "serious" are not synonymous. Severity refers to the intensity of an AE (e.g., rated as mild, moderate, or severe, or according to National Cancer Institute Common Terminology Criteria for Adverse Events [NCI CTCAE]; see Section 5.3.3); the event itself may be of relatively minor medical significance (such as severe headache without any further findings).

Severity and seriousness need to be independently assessed for each AE recorded on the eCRF.

Serious AEs are required to be reported by the Investigator to the Sponsor immediately (i.e., no more than 24 hours after learning of the event; see Section 5.4.2 for reporting instructions).

[REDACTED]

[REDACTED]

[REDACTED]

[REDACTED]

[REDACTED]

[REDACTED]

[REDACTED]

[REDACTED]

[REDACTED]

[REDACTED]

[REDACTED]

█ [REDACTED]

█ [REDACTED]

5.3 METHODS AND TIMING FOR CAPTURING AND ASSESSING SAFETY PARAMETERS

The Investigator is responsible for ensuring that all AEs (see Section 5.2.1 for definition) are recorded on the Adverse Event eCRF and reported to the Sponsor in accordance with instructions provided in this section and in Sections 5.4–5.6.

For each AE recorded on the Adverse Event eCRF, the Investigator will make an assessment of seriousness (see Section 5.2.2 for seriousness criteria), severity (see Section 5.3.3), and causality (see Section 5.3.4).

5.3.1 Adverse Event Reporting Period

Investigators will seek information on AEs at each subject contact. All AEs, whether reported by the subject or noted by study personnel, will be recorded in the subject's medical record and on the Adverse Event eCRF (and Form, if appropriate).

After informed consent has been obtained but prior to initiation of study drug, only SAEs caused by a protocol-mandated intervention (e.g., invasive procedures such as biopsies, discontinuation of medications) should be reported (see Section 5.4.2 for instructions for reporting SAEs).

After initiation of study drug, all AEs will be reported until up to 21 days after the last dose of study drug.

Instructions for reporting AEs that occur after the AE reporting period are provided in Section 5.6.

5.3.2 Eliciting Adverse Event Information

A consistent methodology of non-directive questioning should be adopted for eliciting AE information at all subject evaluation timepoints. Examples of non-directive questions include the following:

"How have you felt since your last clinic visit?"

"Have you had any new or changed health problems since you were last here?"

5.3.3 Assessment of Severity of Adverse Events

Table 2 provides guidance for assessing AE severity.

Table 2 Adverse Event Severity Grading Scale

Severity	Description
Mild	Discomfort noticed, but no disruption of normal daily activity
Moderate	Discomfort sufficient to reduce or affect normal daily activity
Severe	Incapacitating with inability to work or to perform normal daily activity

Note: Regardless of severity, some events may also meet seriousness criteria. Refer to definition of a serious adverse event (see Section 5.2.2).

5.3.4 Assessment of Causality of Adverse Events

Investigators should use their knowledge of the subject, the circumstances surrounding the event, and an evaluation of any potential alternative causes to determine whether an AE is considered to be related to the study drug, indicating "yes" or "no" accordingly.

The following guidance should be taken into consideration (see also Table 3):

- Temporal relationship of event onset to the initiation of study drug
- Course of the event, with special consideration of the effects of dose reduction, discontinuation of study drug, or reintroduction of study drug (as applicable)
- Known association of the event with the study drug or with similar treatments
- Known association of the event with the disease under study
- Presence of risk factors in the subject or use of concomitant medications known to increase the occurrence of the event
- Presence of non-treatment-related factors that are known to be associated with the occurrence of the event

Table 3 Causal Attribution Guidance

Is the adverse event suspected to be caused by the study drug on the basis of facts, evidence, science-based rationales, and clinical judgment?	
YES (RELATED)	There is a plausible temporal relationship between the onset of the adverse event and administration of the study drug, and the adverse event cannot be readily explained by the subject's clinical state, intercurrent illness, or concomitant therapies; and/or the adverse event follows a known pattern of response to the study drug; and/or the adverse event abates or resolves upon discontinuation of the study drug or dose reduction and, if applicable, reappears upon re-challenge.
NO (NOT RELATED)	An adverse event will be considered related, unless it fulfills the criteria specified below. Evidence exists that the adverse event has an etiology other than the study drug (e.g., preexisting medical condition, underlying disease, intercurrent illness, or concomitant medication); and/or the adverse event has no plausible temporal relationship to administration of the study drug (e.g., cancer diagnosed 2 days after first dose of study drug).

For subjects receiving combination therapy, causality will be assessed individually for each protocol-mandated therapy.

5.3.5 Procedures for Recording Adverse Events

Investigators should use correct medical terminology/concepts when recording AEs on the Adverse Event eCRF. Avoid colloquialisms and abbreviations.

Only one AE term should be recorded in the event field on the Adverse Event eCRF.

5.3.5.1 Infusion-Related Reactions

Adverse events that occur during or within 24 hours after study drug administration should be captured as individual signs and symptoms on the Adverse Event eCRF rather than an overall diagnosis (e.g., record dyspnea and hypotension as separate events rather than a diagnosis of infusion-related reaction).

5.3.5.2 Diagnosis versus Signs and Symptoms

For AEs other than infusion-related reactions (see Section 5.3.5.1), a diagnosis (if known) should be recorded on the Adverse Event eCRF rather than individual signs and symptoms (e.g., record only liver failure or hepatitis rather than jaundice, asterixis, and elevated transaminases). However, if a constellation of signs and/or symptoms cannot be medically characterized as a single diagnosis or syndrome at the time of reporting, each individual event should be recorded on the Adverse Event eCRF. If a diagnosis is subsequently established, all previously reported AEs based on signs and symptoms should be nullified and replaced by one AE report based on the single diagnosis, with a starting date that corresponds to the starting date of the first symptom of the eventual diagnosis.

5.3.5.3 Adverse Events That Are Secondary to Other Events

In general, AEs that are secondary to other events (e.g., cascade events or clinical sequelae) should be identified by their primary cause, with the exception of severe or serious secondary events. A medically significant secondary AE that is separated in time from the initiating event should be recorded as an independent event on the Adverse Event eCRF. For example:

- If vomiting results in mild dehydration with no additional treatment in a healthy adult, only vomiting should be reported on the eCRF.
- If vomiting results in severe dehydration, both events should be reported separately on the eCRF.
- If a severe gastrointestinal hemorrhage leads to renal failure, both events should be reported separately on the eCRF.
- If dizziness leads to a fall and consequent fracture, all 3 events should be reported separately on the eCRF.
- If neutropenia is accompanied by an infection, both events should be reported separately on the eCRF.

All AEs should be recorded separately on the Adverse Event eCRF if it is unclear as to whether the events are associated.

5.3.5.4 Persistent or Recurrent Adverse Events

A persistent AE is one that extends continuously, without resolution, between subject evaluation timepoints. Such events should only be recorded once on the Adverse Event eCRF (and Form, if appropriate). The initial severity (intensity or grade) of the event will be recorded at the time the event is first reported. If a persistent AE becomes more severe, the most extreme severity should also be recorded on the Adverse Event eCRF (and Form, if appropriate). If the event becomes serious, it should be reported to the Sponsor immediately (i.e., no more than 24 hours after learning that the event became serious; see Section 5.4.2 for reporting instructions). The Adverse Event eCRF if already completed should be updated by changing the event from "non-serious" to "serious," providing the date that the event became serious, and completing all data fields related to SAEs.

A recurrent AE is one that resolves between subject evaluation timepoints and subsequently recurs. Each recurrence of an AE should be recorded as a separate event on the Adverse Event eCRF (and Form if appropriate).

5.3.5.5 Abnormal Laboratory Values

Not every laboratory abnormality qualifies as an AE. A laboratory test result must be reported as an AE if it meets any of the following criteria:

- Is accompanied by clinical symptoms
- Results in a change in study treatment (e.g., dosage modification, treatment interruption, or treatment discontinuation)
- Results in a medical intervention (e.g., potassium supplementation for hypokalemia) or a change in concomitant therapy
- Is clinically significant in the Investigator's judgment

It is the Investigator's responsibility to review all laboratory findings. Medical and scientific judgment should be exercised in deciding whether an isolated laboratory abnormality should be classified as an AE.

If a clinically significant laboratory abnormality is a sign of a disease or syndrome (e.g., alkaline phosphatase and bilirubin $5 \times$ ULN associated with cholestasis), only the diagnosis (i.e., cholestasis) should be recorded on the Adverse Event eCRF (and Form if appropriate).

If a clinically significant laboratory abnormality is not a sign of a disease or syndrome, the abnormality itself should be recorded on the Adverse Event eCRF (and Form if appropriate), along with a descriptor indicating whether the test result is above or below the normal range (e.g., "elevated potassium," as opposed to "abnormal potassium"). If

the laboratory abnormality can be characterized by a precise clinical term per standard definitions, the clinical term should be recorded as the AE. For example, an elevated serum potassium level of 7.0 mEq/L should be recorded as "hyperkalemia."

Observations of the same clinically significant laboratory abnormality from visit to visit should only be recorded once on the Adverse Event eCRF (see Section 5.3.5.4 for details on recording persistent AEs).

5.3.5.6 Abnormal Vital Sign Values

Not every vital sign abnormality qualifies as an AE. A vital sign result must be reported as an AE if it meets any of the following criteria:

- Is accompanied by clinical symptoms
- Results in a change in study treatment (e.g., dosage modification, treatment interruption, or treatment discontinuation)
- Results in a medical intervention or a change in concomitant therapy
- Is clinically significant in the Investigator's judgment

It is the Investigator's responsibility to review all vital sign findings. Medical and scientific judgment should be exercised in deciding whether an isolated vital sign abnormality should be classified as an AE.

If a clinically significant vital sign abnormality is a sign of a disease or syndrome (e.g., high blood pressure), only the diagnosis (i.e., hypertension) should be recorded on the Adverse Event eCRF (and Form if appropriate).

Observations of the same clinically significant vital sign abnormality from visit to visit should only be recorded once on the Adverse Event eCRF (see Section 5.3.5.4 for details on recording persistent AEs).

5.3.5.7 Abnormal Liver Function Tests

The finding of an elevated ALT or AST ($>3 \times \text{ULN}$) in combination with either an elevated total bilirubin ($>2 \times \text{ULN}$) or clinical jaundice in the absence of cholestasis or other causes of hyperbilirubinemia is considered to be an indicator of severe liver injury (as defined by Hy's Law). Therefore, Investigators must report as an AE the occurrence of either of the following:

- Treatment-emergent ALT or AST $>3 \times \text{ULN}$ in combination with total bilirubin $>2 \times \text{ULN}$
- Treatment-emergent ALT or AST $>3 \times \text{ULN}$ in combination with clinical jaundice

The most appropriate diagnosis or (if a diagnosis cannot be established) the abnormal laboratory values should be recorded on the Adverse Event eCRF (see Section 5.3.5.2) and reported to the Sponsor immediately (i.e., no more than 24 hours after learning of the event), either as a SAE or an AE of special interest (see Section 5.4.2).

5.3.5.8 Deaths

All deaths that occur during the protocol-specified AE reporting period (see Section 5.3.1), regardless of relationship to study drug, must be recorded on the Adverse Event eCRF and immediately reported to the Sponsor (see Section 5.4.2).

Death should be considered an outcome and not a distinct event. The event or condition that caused or contributed to the fatal outcome should be recorded as the single medical concept on the Adverse Event eCRF. Generally, only one such event should be reported. If the cause of death is unknown and cannot be ascertained at the time of reporting, **"unexplained death"** should be recorded on the Adverse Event eCRF. If the cause of death later becomes available (e.g., after autopsy), "unexplained death" should be replaced by the established cause of death. The term **"sudden death"** should not be used unless combined with the presumed cause of death (e.g., "sudden cardiac death").

Deaths that occur after the AE reporting period should be reported as described in Section 5.6.

5.3.5.9 Preexisting Medical Conditions

A preexisting medical condition is one that is present at the screening visit for this study. Such conditions should be recorded on the General Medical History and Baseline Conditions eCRF.

A preexisting medical condition should be recorded as an AE only if the frequency, severity, or character of the condition worsens during the study. When recording such events on the Adverse Event eCRF, it is important to convey the concept that the preexisting condition has changed by including applicable descriptors (e.g., "more frequent headaches").

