3. STUDY DESIGN

3.1 DESCRIPTION OF THE STUDY

This study will be a non-randomized, open-label, parallel group, two-treatment study in healthy volunteers to investigate the absolute oral bioavailability of balovaptan. The study will be conducted at 1 site in the Netherlands.

Screening

Screening will be conducted up to 28 days prior to admission to the clinical research unit (CRU).

In-Clinic Confinement

Subjects will be in the CRU for 2 study periods. In both periods, subjects will be admitted on Day -1 (the day before dosing begins). Day 1 will be the first day of dosing. In Period 1, subjects will be discharged on Day 10 after all assessments have been completed. There will be a wash-out period of 14 days between Day 1 of Period 1 and Day 1 of Period 2.

Subjects will be readmitted to the CRU for a second in-house period on Day 14 of Period 1 (Day -1 of Period 2) to begin Period 2. Day 1 will be the first day of dosing. In Period 2, subjects will be discharged in the morning of Day 19.

During the in-house stays and screening and follow-up visits, subjects will undergo assessments as outlined in the schedule of activities ([Appendix 1](#)), including assessments of AEs and concomitant medications, vital signs, electrocardiograms (ECGs), clinical laboratory evaluations, and blood sampling for PK evaluations. ■

Dosing

Two cohorts of 8 subjects each will be included in the study. The 2 cohorts will receive the following treatment regimens:

Cohort 1

Period 1:

- Day 1: a single oral dose of 10 mg balovaptan after at least 10 hours of fasting, followed 1.25 hours later by a 15-minute intravenous (IV) infusion of [¹³C]-labeled balovaptan 0.1 mg.

Period 2:

- Day 1 to Day 14: oral doses of 10 mg balovaptan QD; on Day 7 and Day 14 study drug administration will take place after at least 10 hours of fasting.
- Day 14: the final oral dosing will be followed 1.25 hours later by a 15-minute IV infusion of [¹³C]-labeled balovaptan 0.1 mg.

Cohort 2

Period 1:

- Day 1: a single oral dose of 50 mg balovaptan after at least 10 hours of fasting, followed 1.25 hours later by a 15-minute IV infusion of [¹³C]-labeled balovaptan 0.1 mg.

Period 2:

[figure not shown]
- Day 1 to Day 14: oral doses of 50 mg balovaptan QD; on Day 7 and Day 14 study drug administration will take place after at least 10 hours of fasting.
- Day 14: the final oral dosing will be followed 1.25 hours later by a 15-minute IV infusion of [¹³C]-labeled balovaptan 0.1 mg.

Follow-up

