### 17.1.1 Adverse Events

All AEs will be coded to the current version of Medical Dictionary for Regulatory Activities (MedDRA, the latest version) by F. Hoffmann-La Roche, Ltd.

All AE summaries will include only treatment emergent adverse events (TEAEs). Treatment-emergent adverse events are those which occur after the first dose of study drug. AEs starting prior to medication dosing in the first period will be regarded as pre-dose AEs (i.e. non-TEAEs).

TEAEs occurring following dosing in a specific analysis period but before dosing in the next analysis period will be attributed to that specific analysis period, thus to the last received treatment. If the time is missing for an AE on a dosing day then the AE will be attributed to the treatment given on that day.

All AEs (including non-TEAEs) recorded on the eCRF will be listed (including analysis period and treatment information). Pre-dose AEs will be presented in a separate listing. In addition, a separate listing of AEs leading to withdrawal from study will be provided.

TEAEs will be tabulated by system organ class and preferred term: one table with all TEAEs (number and percentage of subjects) overall and by treatment; one table with related TEAEs (number and percentage of subjects) overall and by treatment; one table with all TEAEs (number and percentage of subjects) by treatment and relationship to study drug; one table with TEAEs (number and percentage of subjects) by treatment and severity.

Subjects are counted once, per preferred term per treatment, for the most severe of multiple occurrences (in case of severity) or most drug-related event (in case of relationship) of a specific MedDRA term. AEs whose causal relationship was characterized as 'Yes'/'No' will be regarded as being related/not related to the study medication.

The following missing data will be imputed as defined (for calculations only / will not be presented):

- Missing AE start and / or end times for the calculation of onset and duration will be assumed to be at 00:01 for a start time and 23:59 for end times

- Missing AE severity or relationship will be assumed to be severe or related, respectively
- Missing AE start times for the determination of treatment emergence will be assumed to occur after treatment unless partial date documents the AE as happening prior to treatment

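### Treatment emergence is set by start date alone and preexisting conditions are fixed at the screening visit, so a condition that begins before the first dose and worsens on drug may be misclassified in the TEAE tables

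*Protocol*

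**What the plan says.** - **Protocol 5.3.5.9:** "A preexisting medical condition is one that is present at the screening visit for this study". Such a condition goes on the General Medical History and Baseline Conditions eCRF and becomes an AE only if it gets worse during the study.
- **Protocol 5.3.1:** The section opens by requiring every AE found at any subject contact to be entered in the medical record and on the AE eCRF. For the time between consent and first dose it then says that "only SAEs caused by a protocol-mandated intervention (e.g., invasive procedures such as biopsies, discontinuation of medications) should be reported". From the first dose the rule widens: "After initiation of study drug, all AEs will be reported until up to 21 days after the last dose of study drug".
- **Protocol 5.2.1:** Events caused by a protocol procedure are AEs, "including those that occur prior to assignment of study treatment". Worsening of a known condition is also an AE.
- **Protocol 5.3.5.4:** A persistent AE is entered once, with its first severity and, if it worsens, its most extreme severity.
- **SAP 17.1.1:** All AE summaries are restricted to TEAEs, and the boundary is the start: "AEs starting prior to medication dosing in the first period will be regarded as pre-dose AEs (i.e. non-TEAEs"). It adds: "Pre-dose AEs will be presented in a separate listing". The section has no clause on worsening.
- **SAP 9.2.1:** Baseline for post-dose evaluations is the final observation ahead of the first Period 1 dose.

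**The concern.** The protocol and the SAP use different reference points for what a subject brings to the first dose. For medical conditions it is the screening visit. For the SAP's post-dose evaluations it is the last pre-dose observation. A non-serious condition that begins in between falls under neither rule cleanly. A realistic case is a headache on Day -1, when Protocol 4.4.3 has already stopped methylxanthines; headache is also the protocol's own example of a worsening condition.

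Safety and tolerability is a secondary objective, and the study is open-label with no placebo group. The pre-dose state is therefore the only within-study reference for what is new on drug. If the same clinical course can be tabulated or not depending on when it began relative to screening, or on how the site dated the entry, the TEAE percentages are not fully interpretable.

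**Working it through.** **Length of the interval.** Protocol 3.1 allows screening up to 28 days before admission and places admission one day before dosing. The longest interval from screening to first dose is 28 + 1 = 29 days. This is a maximum, not a typical value.

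**Following a condition through the rules.**

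| Course | How it can be recorded | Result under SAP 17.1.1 |
|---|---|---|
| Present at screening, worsens after first dose | Baseline eCRF, then an AE for the worsening (5.3.5.9) | TEAE, if dated at the worsening |
| Begins after screening, recorded as a pre-dose AE, persists and worsens on drug | One record with a pre-dose start; worst severity added (5.3.5.4) | Non-TEAE: listed, absent from all AE tables |
| Begins after screening, entered as a baseline condition, worsens on drug | AE under 5.2.1, dated at the worsening | TEAE |
| Begins after screening, not recorded before dosing, unchanged on drug, first noted after dosing with no start date | AE with missing start date | Attributed to Period 1 treatment, so counted as a TEAE |

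The first and second rows differ only in whether the condition began before or after screening, yet one is tabulated and the other is not. The second and third differ only in the form the site used. The fourth is the opposite error: a condition that the drug did not change is counted as new.

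**Can the second row occur?** It needs a non-serious AE recorded before dosing. The opening of 5.3.1, the inclusion of pre-treatment events in 5.2.1, the AE assessments that Protocol 3.1 places in the screening visit and in-house stays, and the SAP's planned pre-dose listing all point that way. The pre-dose sentence of 5.3.1 points the other way. If it governs recording as well as reporting, the second row disappears, the fourth becomes more likely, and the SAP listing can hold nothing but procedure-caused SAEs.

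**Size per subject.** SAP 9.1.3 bases percentages on subjects exposed within a treatment. With 8 per cohort, one reclassified subject moves a treatment percentage by 1/8 = 12.5 points. In the overall column, with 16 subjects, it is 1/16 = 6.25 points. These figures hold for any one-subject error in groups of this size; they do not measure how likely the error is.

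**The case against.** The strongest case on the other side has four parts.

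1. **Worsening is already an AE.** Protocol 5.2.1 makes worsening of a known condition an AE whenever it began, and 4.5.3 sends clinically significant worsened findings to the AE form. Entered with the date of worsening, it is a TEAE. This stands, and it limits the omission to events carried on one record with the earlier start date. But neither document says that worsening is dated separately or that it overrides the single-record rule.
2. **A baseline record is possible.** Protocol 4.5.2 and 4.5.3 call for medical history and abnormalities to be recorded at baseline, and Day -1 ECG, vital signs, hematology and biochemistry are taken. This also stands, so the accurate statement is that a record is not assured. The protocol does not define baseline, and 5.3.5.9 points to screening. Only the footnotes of the Appendix 1 grid could be read, so I make no claim about whether a Day -1 history or AE check is scheduled.
3. **Pre-dose AEs are not plainly barred.** A reader might infer from 5.3.1 that no non-serious event can be entered before dosing. The section's opening sentences do not support that: the restriction is on what is reported, and it refers to the SAE reporting section. Because 5.3.1 uses the same verb for all post-dose AEs, the text remains ambiguous.
4. **The practical effect is small.** All AEs are listed, including non-TEAEs, and worst severity is kept. Exclusion criteria on illness, ECG and laboratory findings remove many of the more important conditions arising after screening. Safety is descriptive and no hypothesis is tested. All of this stands, and it keeps the point to one of clear classification.

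**Conclusion.** The concern holds in a limited form. Under the stated rules, a non-serious AE recorded with a pre-dose start that worsens on drug is listed but left out of every AE table. A condition arising between screening and first dose (at most 29 days) has no assured baseline record and no explicit worsening rule, so it may be left out of the TEAE tables or wrongly added to them.

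A reader might go further and conclude that such a condition can have no baseline record at all and will always drop out of the tables. The documents do not support this. A baseline entry is allowed, worsening is an AE in its own right, and a worsening entered with its own date is a TEAE. The two halves of that conclusion also pull apart: dropping out through the single-record rule needs a pre-dose record, which the first half says cannot exist.

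The size is 12.5 percentage points per affected subject in a treatment group of 8. The frequency cannot be estimated from the documents. The primary analysis, absolute bioavailability of the 10 mg single dose, does not use AE classification and is unaffected. The verdict assumes that sites follow 5.3.5.4 as written and that no eCRF completion guideline outside these documents settles how worsening is dated.

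**What to change.** 1. **SAP 17.1.1:** define a TEAE as an event that starts after the first dose, or that worsens in severity after the first dose from its pre-dose level, with the worsening dated at its own onset. Protocol 5.3.5.4 mentions severities but no date for a change in severity, so data management should confirm where that date will come from.
2. **Protocol 5.3.5.9:** define a preexisting condition as one present before the first dose of study drug, recorded on the General Medical History and Baseline Conditions eCRF. This brings it into line with SAP 9.2.1.
3. **Protocol 5.3.1:** state which pre-dose events are recorded and which are reported, so that the section agrees with 5.2.1 and with the SAP's planned pre-dose listing. This is a request to reconcile the texts, not to widen collection.

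The cost is minor wording changes and a few extra baseline entries for 16 subjects, with no new visits or procedures. The protocol wording would go through the amendment process in Protocol 9.6. The SAP sentence can be changed alone and on its own removes the omission from the tables, provided the date of worsening is available.
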